3.2 Secondary outcome measures

3.2.1 Exploratory Outcome Measures

- Measurement of treatment adherence to the PRO 140 monotherapy regimen; this will be assessed using number of missed PRO 140 administrations
- Loss of future drug options

The first occurrence of intermediate to high level resistance to any one or more of the standard antiretroviral drugs to which the patient's virus was considered to be sensitive at trial entry (i.e. excluding drug resistance present at baseline).

 - GenoSure Archive Assay will be performed at Baseline.
 - PhenoSense® GT (PhenoSense Integrase and GeneSeq Integrase testing, if applicable), will be performed at the time of virologic failure.
- Proportion of participants overall and within each treatment group experiencing emerging resistance exhibited by fold increase in maraviroc and PRO 140 FC (Fold Change in IC₅₀ and IC₉₀ relative to wild-type virus) between baseline and the time of virologic failure, as a measure of post-baseline phenotypic resistance
 - The data will be from PhenoSense® Entry Assay

3.2.2 Central Nervous System (CNS) sub-study: In a subset of participants (n=20)

- Level of HIV-1 RNA in CSF at T1 (prior to first dose of PRO 140), T4 and VF visits
- PRO 140 concentration in CSF at T1 (prior to first dose of PRO 140), T4 and VF visits
- Relationship between PRO 140 concentration in plasma and CSF
- Relationship between PRO 140 concentration in CSF and HIV-1 RNA in CSF
- Relationship between plasma and CSF HIV-1 RNA suppression and HIV disease progression and safety parameters (i.e., adverse events and laboratory abnormalities)

3.2.3 Genitourinary (GU) sub-study: In a subset of participants (n=20):

- Level of HIV-1 RNA in genital secretion at T1 (prior to first dose of PRO 140), T4, T16 and VF visits.
- PRO 140 concentration in genital secretion at T1 (prior to first dose of PRO 140), T4, T16 and VF visits.
- Relationship between PRO 140 concentration in plasma and genital secretion
- Relationship between PRO 140 concentration and HIV-1 RNA in genital secretion,
- Relationship between plasma and genital secretion HIV-1 RNA suppression and HIV disease progression and safety parameters (i.e., adverse events and laboratory abnormalities)

4. SAMPLE SIZE DETERMINATION AND RATIONALE

Approximately 500 subjects will be enrolled or randomized, in this study. A total of 100 subjects will be randomized to receive PRO 140 700 mg. The sample size is selected on the basis of clinical judgment.

5. RANDOMIZATION AND BLINDING

There were no blinding requirements planned for this study.

The first ~150 eligible subjects were enrolled to receive PRO 140 350mg SC weekly injection in a single-arm study. Subsequently, next ~150 subjects were randomized 1:1 to PRO 140 350mg (Group A) or PRO 140 525mg (Group B). An additional ~200 subjects will be randomized 1:1 to PRO 140 525mg (Group B) or PRO 140 700mg (Group C).

➤ For the first ~150 enrolled subjects:

- **Part 1:** 48-week, single-arm, open-label treatment phase
 - PRO 140 350mg SC weekly injection (Group A)

- **For the subsequent ~150 enrolled subjects:**
 - **Part 1:** 48-week, randomized, two-arm, open-label treatment phase
 - PRO 140 350mg SC weekly injection (Group A)
 - PRO 140 525mg SC weekly injection (Group B)
- **For the subsequent ~200 enrolled subjects:**
 - **Part 1:** 48-week, randomized, two-arm, open-label treatment phase
 - PRO 140 525mg SC weekly injection (Group B)
 - PRO 140 700mg SC weekly injection (Group C)

6. ANALYSIS POPULATIONS

6.1 Intent-to-Treat Population

The Intent-to-Treat (ITT) population is defined as the set of subjects who were enrolled or randomized and have at least one dose of PRO 140.

6.2 Per Protocol Population

The Per Protocol (PP) population is defined as the set of subjects who meet the ITT population requirements, and were not associated with a major protocol violation.

6.3 Safety Population

The Safety population is defined as all subjects who received at least one dose of PRO 140. This population will be used for the analysis of safety parameters.

7. DATA CONVENTION AND RELATED DEFINITIONS

7.1 Baseline Definition

For all parameters, baseline will be defined as the last available value prior to initiation of the first dose of PRO140.

7.2 Duplicate Data

For unplanned duplicate data within a protocol-specified visit, the last measured value will be used for the analysis. If it is not possible to identify the “last measured value” the average of the duplicate values will be used.

No data will be excluded. All collected data will be listed.

7.3 Handling of Missing Data

There are no inferential statistics planned for this study, hence all data will be presented without imputation.

7.4 Multiple Comparisons and Type I Error Rate Multiplicity adjustments

There are no inferential statistics planned for this study, hence there will be no adjustment for multiple comparisons.

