8.2.2.1 Proportion of participants experiencing virologic failure at the assigned dose

The percentages of subjects with virologic failure (as defined in [Section 7.5.6](#)) will be presented descriptively by treatment groups for the ITT and PP populations.

Note: Assigned dose refers to the dose allocated at the time of randomization/enrollment.

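### The SAP pre-specifies no confidence interval for any efficacy proportion and no dose difference within either randomised cohort; its tables by dose mix randomised and non-randomised subjects.

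*SAP*

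**What the plan says.** SAP section 7.4 reads: "There are no inferential statistics planned for this study, hence there will be no adjustment for multiple comparisons". Section 7.3 gives the same reason for presenting data without imputation. Section 8.1 limits categorical outcomes to counts and percentages. Under section 8.2.2.1 the percentages with virologic failure "will be presented descriptively by treatment groups for the ITT and PP populations". Section 8.2.2.2 summarises time to failure by n, mean, SD, median, minimum and maximum. Protocol section 8.7.4 adds Kaplan-Meier plots, and 8.7.4.1 leaves the methods for the primary analysis to the SAP. Neither document names a confidence interval, risk difference, risk ratio or hazard ratio for any outcome.

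On allocation, SAP section 5 describes three successive cohorts:

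- First: "The first ~150 eligible subjects were enrolled to receive PRO 140 350mg SC weekly injection in a single-arm study".
- Second: about 150 subjects randomised 1:1 to 350 or 525 mg.
- Third: about 200 subjects randomised 1:1 to 525 or 700 mg.

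SAP section 4 gives the total: "Approximately 500 subjects will be enrolled or randomized, in this study". It adds: "A total of 100 subjects will be randomized to receive PRO 140 700 mg". The basis is stated plainly: "The sample size is selected on the basis of clinical judgment".

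**The concern.** Protocol section 1.5 attributes viral rebound on 350 mg mainly to too low a dose and expects fewer subjects with low troughs on 525 and 700 mg. Two of the three cohorts were then randomised between adjacent doses. That gives two unconfounded dose contrasts, and the SAP plans to report neither.

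Instead, the columns are dose groups. Subjects enrolled at different times, under different allocation schemes, share a column, so a difference between columns can reflect changes in sites, patients or management as well as dose. No interval accompanies any percentage. A reader is left with three point estimates that look like a dose response and nothing to show how precise they are. Choosing to run no tests does not require this, since estimation with intervals involves no test and no multiplicity adjustment.

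**Working it through.** **1. The plan's own figures.** 150 + 150 + 200 = 500, matching the stated total. 200 / 2 = 100 on 700 mg, matching the stated arm. Randomised: 150 + 200 = 350, as two contrasts of about 75 vs 75 (150 / 2) and 100 vs 100. 350 and 700 mg are never randomised against each other. No alpha, power or effect size is given, so there is no power calculation to reproduce.

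**2. What the dose columns contain.**

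| Group | Cohort 1 (single arm) | Cohort 2 (randomised) | Cohort 3 (randomised) | Total |
|---|---|---|---|---|
| A, 350 mg | ~150 | ~75 | – | ~225 |
| B, 525 mg | – | ~75 | ~100 | ~175 |
| C, 700 mg | – | – | ~100 | ~100 |

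Two thirds of Group A (150 / 225) was not randomised.

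**3. Assumptions for precision.** No dropout, 95% level, and assumed failure rates. The only anchor in the protocol is the earlier 350 mg study (section 1.4.2.7): 23 of 43 completed 12 weeks without failure, so at most 20/43 = 47% failed. That study used a 400 copies/mL threshold and a much shorter period, so it suggests a range and no more.

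**4. Single proportions.** Wilson interval: [p + z²/2n ± z√(p(1−p)/n + z²/4n²)] / (1 + z²/n), z = 1.96.

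- 40% of 75: 30% to 51%
- 40% of 100: 31% to 50%
- 20% of 100: 13% to 29%

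**5. Differences (lower dose minus higher dose).** Newcombe interval, with d = p1 − p2 and Wilson limits l and u:

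- lower = d − √[(p1 − l1)² + (u2 − p2)²]
- upper = d + √[(u1 − p1)² + (p2 − l2)²]

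For 30% vs 20% at 100 per arm, the Wilson limits are 21.89 to 39.58 and 13.34 to 28.88.

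- Lower: 10 − √(8.11² + 8.88²) = 10 − 12.03 = −2.0
- Upper: 10 + √(9.58² + 6.66²) = 10 + 11.67 = +21.7

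| Failure rates | Per arm | Difference | 95% Newcombe interval (points) |
|---|---|---|---|
| 40% vs 30% | 75 | 10 | −5.2 to +24.6 |
| 40% vs 30% | 100 | 10 | −3.2 to +22.7 |
| 30% vs 20% | 100 | 10 | −2.0 to +21.7 |
| 20% vs 10% | 100 | 10 | 0.0 to +19.9 |
| 15% vs 5% | 100 | 10 | +1.6 to +18.8 |

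30% of 75 is not a whole number of subjects; 22/75 in its place gives −4.5 to +25.2.

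**6. What the pooled columns would suggest.** At 40% vs 30%, Group A (225) vs Group B (175) gives about +0.5 to +19.1. The randomised 75 vs 75 contrast with the same rates gives −5.2 to +24.6. The pooled interval excludes zero, but it rests largely on subjects who were not randomised between those doses.

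**The case against.** The strongest reply is that this is a declared choice. The objective is clinical safety and treatment strategy, no dose comparison is listed as an objective, and the sample size makes no claim to power. Section 7.4 is also internally correct: with no tests there is nothing to adjust. That stands, and the absence of hypothesis tests is not an error. It does not explain leaving out intervals, which a descriptive report can carry.

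A reader might infer that the trial will be unable to tell whether an observed dose difference exceeds chance. The documents do not support that. Counts by group will be tabulated and all data listed by subject, so a crude interval can be worked out afterwards. What is missing is a pre-specified output. But the crude interval from the planned tables would be the pooled one in step 6; the within-cohort contrast would have to be rebuilt from listings.

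A reader might also infer that any 10-point difference would be compatible both with no effect and with more than 20 points. That depends on the failure rates. At 100 per arm, 15% vs 5% excludes zero and stays below 20 points.

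Finally, the protocol's Kaplan-Meier plots would show failure over time. The SAP does not carry them forward, and neither document attaches intervals to them, so they soften the point only slightly.

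**Conclusion.** The concern holds as a gap in pre-specified estimation. The SAP plans no interval for any efficacy proportion, no risk difference in either randomised cohort, and no table that separates the cohorts. If failure rates lie around 20–40%, the randomised contrasts would have intervals about 24 to 30 points wide for a 10-point difference, which bare percentages would hide. At lower rates precision is better.

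This rests on the assumed rates, no dropout, and the cohort structure in SAP section 5, which the protocol synopsis and protocol section 3 share. Protocol section 4 instead describes the first 300 subjects as all randomised 1:1 between 350 and 525 mg, and protocol section 8.3 gives 300 as the total. If section 4 were right, the first contrast would be about 150 vs 150 (300 / 2), so the randomised sets cannot be fixed until these statements agree. The change should be made before analysis; nothing here calls the conduct of the trial into question.

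**What to change.** 1. Reconcile protocol sections 4 and 8.3 with SAP section 5, and define each randomised set explicitly.
2. In SAP 7.3 and 7.4, replace the blanket statement with wording to this effect: *no hypothesis tests; estimation with 95% intervals*.
3. Add Wilson 95% intervals to the proportions in 8.2.2.1, 8.2.2.4, 8.2.2.6 and 8.2.2.8.
4. Tabulate efficacy by enrolment cohort as well as by dose.
5. Report risk differences with Newcombe 95% intervals for virologic failure and for HIV-1 RNA <50 copies/mL at weeks 24 and 48. Do this only within the second cohort (525 vs 350 mg) and within the third (700 vs 525 mg).

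The cost is a few lines of SAP text, some code and a few more tables, with no extra patients. The intervals will be wide, and the report will have to say so.

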7.5 Standard Calculations

7.5.1 Age

Age will be calculated as the number of completed years between the date of informed consent and the subject's birth date.

$$\text{Age (years)} = \text{integer of}[(\text{date of informed consent} - \text{date of birth}) / 365.25]$$

7.5.2 Body Mass Index (BMI)

BMI will be calculated using height (in cm) and weight (in kg) according to the formula noted below.

$$\text{BMI (kg/m}^2\text{)} = \text{weight (kg)} / [(\text{height (cm)} / 100)^2]$$

7.5.3 Change from Baseline

For any of the effectiveness measurements change from baseline will be calculated using the formula noted below.

$$\text{Change from baseline} = \text{Post Baseline Measurement} - \text{Baseline Measurement}$$

7.5.4 Virologic Failure

Virologic failure is defined as two (2) consecutive plasma HIV-1 RNA levels of ≥ 200 copies/mL.

7.5.5 Time to Virologic Failure

The date of virologic failure is defined as the date of the second assessment of the two (2) consecutive plasma HIV-1 RNA levels of ≥ 200 copies/mL when virologic failure is confirmed.

For the censored subjects (i.e., subjects who do not have an event) the date of event will be:

- The time of the last visit data; if the subject completes the trial;

- The time of the early termination for those subjects who withdraw or early terminate from the trial.

[for those with virologic failure]

Time to virologic failure = (Date of first HIV-1 RNA levels of ≥ 200 copies/mL – Date of first treatment) +1

[for those without virologic failure]

Time to virologic failure = (Date of last visit/ early termination – Date of first treatment) +1

7.5.6 Viral Re-suppression

For all subjects with virologic failure, viral re-suppression is defined as having a plasma HIV-1 RNA levels of <50 copies/mL after experiencing virologic failure.

7.5.7 Time to Viral re-suppression

This will be assessed for all subjects experiencing virologic failure. The date of viral re-suppression is defined as the date of first assessment where plasma HIV-1 RNA levels of <50 copies/mL after virologic failure.

Time to viral re-suppression = (Date of first HIV-1 RNA levels of < 50 copies/mL – Date of virologic failure) +1

7.5.8 Time to Viral re-suppression after re-initiation of oral combination antiretroviral regimen (Re-ART)

This will be assessed for all subjects experiencing virologic failure and oral combination antiviral therapy is re-initiated. The date of viral re-suppression is defined as the date of first assessment where plasma HIV-1 RNA levels of <50 copies/mL after virologic failure.

Time to viral re-suppression after Re-ART = (Date of first HIV-1 RNA levels of < 50 copies/mL – Date of first re-initiation of oral combination regimen) +1

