#### **8.7.4 Efficacy Analysis**

All data from the primary and secondary outcome measures will be summarized and tabulated according to the variable type:

- Time to event data will be depicted using Kaplan-Meier plots
- Continuous data summaries will include number of observations, mean, standard deviation, median, and minimum and maximum values.
- Categorical data summaries will include frequency counts and percentages.

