- [19] Monogram Biosciences Trofile[®] DNA or RNA assay (or both) will be performed at the Virologic Failure Visit depending on the last known HIV-1 RNA levels
- [20] Should VF occur, Group A or Group B subjects may transition to high dose IP and continue in 48-week Treatment Phase
- [21] To assess the number CCR5 receptors on patients' CD4 cell surface, and number and percentage of CCR5 receptors that are covered by PRO 140. Sites should not collect samples on Fridays, since InCellDx lab cannot receive samples on Saturdays.
- [22] No new sample collection needed. The residual whole blood sample collected for tropism assessment at Screening or at post-treatment visits will be used for testing of CCR5 genotyping (homozygous or heterozygous status).

Table 2-3: Schedule of Assessments –Follow-Up (FU) Phase

(a) Subjects who do NOT experience Virologic Failure

Procedure/Assessments	Follow-Up Visit -1	Follow-Up Visit -2
	NVF-FU1	NVF-FU2
	2 weeks (±3 days) after T48	4 weeks (±3 days) after T48
Physical Examination	X ^[1]	X ^[1]
Vital Signs	X	X
Plasma HIV-1 RNA level	X	X
TruCount T assay	X	X
Anti-idiotypic Antibodies to PRO 140		X
Re-initiate combination Antiretroviral Therapy	X	X
Adverse Events	X	X
Concomitant Medications	X	X

[1] Symptom-directed physical examination

(b) Subjects who experience Virologic Failure

- Short-Term Follow-Up Visits

Procedure/Assessments	Follow-Up Visit -1	Follow-Up Visit -2	Follow-Up Visit -3 ^[1]
	VF-FU1	VF-FU2	VF-FU3
	4 weeks (±7 days) after VF visit	8 weeks (±7 days) after VF visit	12 weeks (±7 days) after VF visit
Physical Examination	X ^[2]	X ^[2]	X ^[2]
Vital Signs	X	X	X
Plasma HIV-1 RNA level	X	X	X
TruCount T assay	X	X	X
Anti-idiotypic Antibodies to PRO 140	X		
Re-initiate combination Antiretroviral Therapy	X	X	X
Adverse Events	X	X	X
Concomitant Medications	X	X	X

[1] Subject will be followed up every 4 weeks until viral suppression is achieved (i.e., plasma HIV-1 RNA levels decline to < 50 copies/mL). Subject will undergo additional follow-up visits every 4 weeks beyond VF-FU3 visit (up to a maximum of 6 months after re-initiation of combination antiviral therapy), if viral suppression is not achieved at the end of VF-FU3 visit.

[2] Symptom-directed physical examination

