8.2.2.3 Proportion of participants moved to rescue arm or higher dose group

The percentages of subjects moved to a rescue arm or higher dose will be presented descriptively by treatment groups for the ITT and PP populations.

Note: Rescue is defined as subjects who were unable to maintain viral suppression, or experienced virologic failure, and moved to a higher dose of PRO 140.

8.2.2.4 Proportion of participants achieving viral re-suppression (HIV-1 RNA <50 copies/mL) during Treatment Phase after moving to rescue arm or higher dose group

The percentages of subjects with virologic re-suppression (as defined in [Section 7.5.8](#)) will be presented descriptively by treatment groups for the subset of the ITT and PP populations that moved to a rescue arm or higher dose group.

8.2.2.5 Time to achieving viral re-suppression (HIV-1 RNA <50 copies/mL) during Treatment Phase for subjects who moved to rescue arm or higher dose group

The number of observations, mean, standard deviation, median, and minimum and maximum values will be presented to summarize time to viral re-suppression (as defined in [Section 7.5.9](#)) by treatment groups for the subset of the ITT and PP populations that moved to a rescue arm or higher dose group.

8.2.2.6 Proportion of participants achieving viral re-suppression (HIV-1 RNA <50 copies/mL) after experiencing virologic failure (during the Treatment and Follow-up Phase)

The percentages of subjects with virologic re-suppression (as defined in [Section 7.5.8](#)) will be presented descriptively by treatment groups for the subset of the ITT and PP populations that experienced virologic failure.

8.2.2.7 Time to achieving viral re-suppression (for virologic failure subjects) after re-initiation of oral combination antiretroviral regimen during the Follow-up Phase.

The number of observations, mean, standard deviation, median, and minimum and maximum values will be presented to summarize time to viral re-suppression after re-initiation of oral combination antiretroviral regimen (as defined in [Section 7.5.10](#)) by treatment groups for the subset of the ITT and PP populations that experienced virologic failure and had re-initiation of oral combination antiviral therapy.

8.2.2.8 Proportion of participants completing 24, 48 weeks of PRO 140 treatment with HIV-1 RNA <50 copies/mL

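### Time to viral re-suppression has no rule for subjects who never re-suppress, so the reported mean and median describe successes only, chiefly in the rescue arm (SAP 8.2.2.5)

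*SAP*

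**What the plan says.** Two of the ten primary efficacy measures (Protocol 8.2.2; SAP 3.1.2) are times to re-suppression: one for subjects moved to a higher dose during the Treatment Phase, and one for failures who restart oral ART.

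SAP 7.5.7 states its population as "This will be assessed for all subjects experiencing virologic failure" and gives one formula: "Time to viral re-suppression = (Date of first HIV-1 RNA levels of < 50 copies/mL – Date of virologic failure) +1". SAP 7.5.8 has the same structure with a different starting date: "Time to viral re-suppression after Re-ART = (Date of first HIV-1 RNA levels of < 50 copies/mL – Date of first re-initiation". In both, the end date is the first RNA below 50 after failure ("The date of viral re-suppression is defined as the date of first assessment where plasma HIV-1 RNA levels of <50 copies/mL after virologic failure").

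For both endpoints (SAP 8.2.2.5 and 8.2.2.7) the planned output is: "The number of observations, mean, standard deviation, median, and minimum and maximum values will be presented to summarize time to viral re-suppression". They cite Sections 7.5.9 and 7.5.10, which do not exist. The numbering is shifted by two, so 7.5.7 and 7.5.8 are meant and no further rule sits behind the references.

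Elsewhere the plan does treat times as time-to-event data. For time to virologic failure, SAP 7.5.5 has a no-event branch: "For the censored subjects (i.e., subjects who do not have an event) the date of event will be" the last visit or early termination. Protocol 8.7.4 says: "Time to event data will be depicted using Kaplan-Meier plots". The SAP plans no such plot for re-suppression.

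**The concern.** A subject who stays at or above 50 copies until rescue ends, or is lost before reaching that level, has no end date and so no value. The stated population is everyone who failed; the population that can be summarized is everyone who recovered. The subjects missing from the mean and median are missing because of a poor outcome.

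The windows are also unequal. Rescue dosing lasts for what is left of the 48 weeks, so a subject who fails late has little time in which a slow response could be seen. If failures come later on one starting dose, that group's reported mean time will be shorter at the same true speed of response. Results are tabulated by treatment group, so a reader could take the difference as a difference between doses.

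**Working it through.** The plan contains no figure to reproduce: no assumed speed of re-suppression, effect size or power, and a sample size set by clinical judgment. The check is therefore a comparison of the definitions, followed by an illustration on stated assumptions.

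**1. Who receives a value**

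| Variable | Value if event | Value if no event |
|---|---|---|
| Time to virologic failure (SAP 7.5.5) | yes | yes, last visit or early termination |
| Time to re-suppression (SAP 7.5.7) | yes | none |
| Time to re-suppression after ART restart (SAP 7.5.8) | yes | none |

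**2. Observation windows**

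Rescue: 48 weeks minus the week of failure. Failure at weeks 8-16 leaves 32-40 weeks; failure at weeks 24-40 leaves 8-24 weeks. After ART restart, visits are 4-weekly until suppression ("up to a maximum of 6 months after re-initiation of combination antiviral therapy"), with RNA again at 6 and 12 months after the failure visit (Protocol 4.4.1.2).

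**3. Continuous reading**

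Assumptions, none from the documents: response time is exponential with median m, so λ = ln 2 / m; everyone can respond; the window is uniform on (a, b) and independent of response.

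- Share re-suppressed: p = 1 − (e^(−λa) − e^(−λb)) / (λ(b − a))
- Successes-only median (when below a): x = −ln(1 − p/2) / λ

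m = 10, λ = 0.06931:
- 32-40 weeks: p = 1 − (0.1088 − 0.0625)/0.5545 = 0.916; x = 8.8
- 8-24 weeks: p = 1 − (0.5743 − 0.1895)/1.1090 = 0.653; x = 5.7

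m = 6, λ = 0.11552:
- 32-40 weeks: p = 1 − (0.0248 − 0.0098)/0.9242 = 0.984; x = 5.9
- 8-24 weeks: p = 1 − (0.3968 − 0.0625)/1.8484 = 0.819; x = 4.6

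**4. Readings every 4 weeks** (the Treatment Phase spacing after week 16)

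Let q = 2^(−4/m). The first reading below 50 falls at week 4k with probability p_k = q^(k−1)(1 − q). It is observed with weight w_k, the chance that the window reaches week 4k. For 32-40 weeks, w = 1 up to week 32 and 0.5 at week 36. For 8-24 weeks, w = 1, 1, 0.75, 0.5, 0.25 at weeks 4 to 20. The successes-only mean is Σ4k·w_k·p_k / Σw_k·p_k.

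- m = 6 (q = 0.6300), 32-40 weeks: 9.913/0.9798 = 10.1
- m = 6, 8-24 weeks: 5.698/0.7741 = 7.4
- m = 10 (q = 0.7579), 32-40 weeks: 11.714/0.9044 = 13.0
- m = 10, 8-24 weeks: 4.931/0.6026 = 8.2

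Untruncated means are 4/(1 − q) = 10.8 and 16.5 weeks. The successes-only median is the first reading by which half the observed successes have occurred. At m = 6, the cumulative share is 0.38 then 0.62 (32-40 weeks) and 0.48 then 0.78 (8-24 weeks), so it is week 8 in both. At m = 10, it reaches 0.47 at week 8 and 0.62 at week 12 (32-40 weeks), but 0.71 by week 8 (8-24 weeks), giving 12 and 8.

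**5. With non-responders censored**

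The chance of not yet being re-suppressed at week 4k is q^k whatever the window. At m = 6, q² = 0.397, so the Kaplan-Meier median is 8 weeks in both windows. At m = 10, q² = 0.574 and q³ = 0.435, so it is 12 weeks in both.

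| True median; reading | Successes-only median, 32-40 / 8-24 wk | Successes-only mean, 32-40 / 8-24 wk | Kaplan-Meier median |
|---|---|---|---|
| 10; continuous | 8.8 / 5.7 | not computed | 10 |
| 6; continuous | 5.9 / 4.6 | not computed | 6 |
| 10; 4-weekly | 12 / 8 | 13.0 / 8.2 | 12 in both |
| 6; 4-weekly | 8 / 8 | 10.1 / 7.4 | 8 in both |

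**The case against.** Four points on the other side carry weight.

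- **The proportions are reported.** SAP 8.2.2.4 and 8.2.2.6 give the percentage re-suppressed by treatment group, and n accompanies each time. A reader might infer that a dose with few but quick responders would pass as the better one. That would require ignoring the adjacent table: in step 3 with m = 10 the share differs visibly, 92% against 65%. What stands is that neither the percentage nor n corrects the mean, the median or the unequal windows.
- **The median is not always affected.** At a true median of 6 weeks with 4-weekly readings it is the same in both windows. At a true median of 4 weeks it is 29 days in fixed windows of 8, 16, 24 and 40 weeks, while the mean runs 38, 50, 54 and 57 days. So the claim that both statistics always look fastest where observation was shortest goes too far.
- **SAP 8.2.2.7 is less exposed.** Follow-up runs until suppression, up to 6 months, with later checks. Protocol 1.4.2.7 reports that all failures with available laboratory data in the earlier work re-suppressed after ART. If that repeats, few subjects drop out of this summary.
- **Everything is descriptive.** No inference or decision rests on these times. That limits the consequence, but a descriptive statistic should still describe its stated population.

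It is also tempting to blame the no-imputation rule in SAP 7.3. Censoring is not imputation, and SAP 7.5.5 censors despite 7.3.

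**Conclusion.** The gap is real: the stated and computable populations differ in SAP 7.5.7 and 7.5.8, and the plan as written gives a successes-only summary. Because SAP 7.5.5 has the missing branch and Protocol 8.7.4 calls for Kaplan-Meier plots, it looks like an omission.

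It matters chiefly for SAP 8.2.2.5. The mean is pulled down where observation is short: in the 4-weekly illustrations, to 7.4 weeks against an untruncated 10.8, and to 8.2 against 16.5. The median is pulled down when response is slow relative to the window. The bias in SAP 8.2.2.7 is probably small. All sizes rest on the assumed exponential shape, the medians of 6 and 10 weeks, and a window unrelated to response speed; only the direction for the mean is robust across the cases run.

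Three stronger readings are not supported:

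- These times are not the primary efficacy outcome; they are two of ten measures.
- If only 60% could ever respond, the all-subject median at m = 10 would be −(10/ln 2)·ln(1 − 0.5/0.6) = 25.8 weeks. The documents give no such ceiling, so this is not an estimate of the bias.
- One cannot assume that subjects who fail again on rescue lack a date. The note in Protocol 4.2 and Sections 4.3 and 5.2.1 place that failure after re-suppression. The synopsis and the text before Table 4-6 carry no such condition.

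**What to change.** 1. Add a no-event branch to SAP 7.5.7 and 7.5.8. Censor at the last HIV-1 RNA of the relevant period: for 8.2.2.5, the last on the rescue dose before any ART restart; for 8.2.2.7, the last follow-up value on ART.
2. Replace the mean and SD with Kaplan-Meier estimates by starting dose: events, number censored, median if reached, and percentage re-suppressed at fixed weeks. Show them beside the proportions from 8.2.2.4 and 8.2.2.6.
3. For 8.2.2.5, stopping rescue or restarting ART without re-suppression may be shown as a competing event, using cumulative incidence. Do not use further failure in that role until the protocol passages named in the verdict are reconciled on whether it can occur before re-suppression.
4. Correct the cross-references to 7.5.9 and 7.5.10, and confirm the starting date of the clock. SAP 7.5.5 defines failure by the second value at or above 200, but its own formula uses the first.

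Cost: SAP wording and standard procedures on data already collected. Reported times will lengthen, and a median may not be reached where windows are short.
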